Funded by the National Institute for Minority Health Disparities (NIMHD 5R01MD010629),⁴ in partnership with the Critical Consciousness Collaborative Board (3CB),⁵ we developed Community Wise (CW), a multi-level manualized behavioral intervention to decrease ASM frequency in a population of self-identified men with histories of substance use disorder (SUD) and incarceration in Essex County, NJ, U.S. The 3CB was founded in 2010 and developed and pilot-tested the original CW. To attain this goal, our team used the multiphase optimization strategy (MOST),⁶ and were guided by community based participatory research (CBPR) principles to develop and optimize CW. MOST is an innovative methodological framework that employs experimental designs to engineer efficient and effective behavioral interventions. MOST guided

the optimization of CW with delivery cost of less than \$2,000 per intervention cycle serving up to ten individuals simultaneously (this was the Medicaid allowable reimbursement cost for SUD group treatment services in 2015).⁷ Clinical trial results showed larger ASM reduction (Cohen's $d=-2.22$, $P=0.067$) in the optimized CW group. Unfortunately, attendance across the 15 intervention sessions was low (only 15% of participants attended 50% of the sessions) and a limitation to the study. Low attendance was due to the intervention's closed group format, the study's randomization strategy, and instability of the study's population (homelessness, poverty).

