In order to improve upon our positive results and to test the intervention with participants who identify as female and do not have a history of incarceration, we propose a pilot study to: 1) identify strategies to improve attendance and reduce ASM, and 2) to test feasibility and acceptability of CW among people with a history of SUD living in marginalized communities. We will achieve these aims by conducting a 2^3 full factorial experiment. This pilot study will strengthen our application for an R01 grant to test CW's effectiveness against standard of care. This pilot will help us identify efficient strategies for improving attendance and, hence, maximize the interventions' effect in reducing ASM. As a highly efficient experimental design, a full factorial experiment will maximize study power and allow us to examine the individual and interactive contributions of each intervention delivery strategy on intervention attendance. MOST will inform which strategies will be retained, thus minimizing waste of resources. The current proposed research will also be conducted in partnership with the 3CB. As our primary individual level outcome, we will use number of sessions attended to pursue the following aim:

Study AIM: To test intervention delivery strategies that effect adequate attendance in CW interventions and marked reduction in ASM. We will test if different intervention delivery strategies will result in a clinically important intervention attendance with a minimum of 50% of participants attending at least 50% of the intervention. We will also compare the effect of different strategies on reducing ASM. Intervention delivery strategies include: 1) Recruiting individuals under supervision (those on parole, drug court, probation, or methadone maintenance); 2) Incentivizing intervention attendance; and 3) Delivering the intervention in an open group format. We will also compare intervention satisfaction measures between intervention strategies.

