**6B. Indicate if your research includes any of the following:**

- Secondary data (use of data collected for purposes other than the current research project)
- Data collected internationally (include [International Research Form](#))
- Translated documents (include [Certificate of Translation Form](#) and translated documents)
- Research activities will take place at Carle (include documentation (email or letter) from Carle stating that the review of your [Research Services Request Form](#) is complete)

6C. Letters of support from outside institutions or entities that are allowing recruitment, research, or record access at their site(s) are attached. Yes Not Applicable

Section 7. PROCEDURES

7A. Select all research methods and/or data sources that apply.

- Surveys or questionnaires, *select all that apply:* Paper Telephone Online
- Interviews
- Focus groups
- Field work or ethnography
- Standardized written, oral, or visual tests
- Taste or smell testing
- Intervention or experimental manipulation
- Exercise and muscular strength testing
- Noninvasive procedures to collect biological specimens (e.g., hair and nail clippings, saliva, etc.)
- Noninvasive procedures to collect physiological data (e.g., physical sensors, electrocardiography, etc.)
- Procedures involving radiation
- Recording audio and/or video and/or taking photographs
- Recording other imaging
- Materials that have already been collected or already exist, *specify source of data:*
- [HIPAA-protected data](#)
- [FERPA-protected data](#)
- [GDPR-protected data](#)
- Other, *please specify:*

7B. List all testing instruments, surveys, interview guides, etc. that will be used in this research.

Drafts or final copies of all research materials are attached. Yes

7C. List approximate study dates. Upon IRB Approval – April 31, 2024

7D. What is the duration of participants' involvement? Participants will complete a 15 minutes study orientation session and two 30 minutes online surveys. They will also be asked to attend 8, two-hour long weekly intervention sessions

7E. How many times will participants engage in research activities? Two times for study activities and 8 times for the intervention.

7F. Narratively describe the research procedures in the order in which they will be conducted.

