People interested in the study will call the study's number. A trained master's level clinician will conduct a brief phone screening to obtain self-reported eligibility on SUD, age, contact information, and whether they are currently under supervision. We will have recruitment quotas of 64 people based on self-reported gender (self-identified as men or woman) and supervision status. Intervention groups will be gender specific following recommendations from the literature and our previous CW pilot study. Phone screened participants will be invited to attend an in-person group orientation session to learn about the study, including randomization procedures and the different forms of CW delivery they may receive. Those interested will be invited to complete the baseline survey online in RedCAP. The survey will include a screening informed consent and an eligibility screen with a computerized Global Appraisal of Individual Needs-Substance Problem Scale (GAIN-SPS).³⁵ Those who are eligible and agree to the procedures will be consented and invited to complete the baseline assessment. Follow-ups will be completed online using RedCAP three months post baseline. Baseline and follow-up will include questions about SUD treatment services received over the past 3 months, the Timeline Follow Back questionnaire to measure alcohol, cannabis, cocaine, opioid, and heroin use in the past 30 days, and demographics. Follow ups will also include intervention satisfaction measures and questions about intervention attendance. Surveys will take 30 minutes to complete. Participants will receive \$20 for baseline and \$30 for follow up assessment. Intervention attendance will be recorded weekly in RedCAP by the peer facilitator. After the baseline assessment, participants will be asked to provide extensive locator information, including formal and informal contacts who can reach the participant in a variety of contingencies. Computer generated randomly permuted blocks will be used to assign participants into one of eight experimental conditions. Randomization will occur in Redcap immediately after completing the baseline and be stratified by gender. The research assistant will call participants after randomization to schedule the group's start date. The attached study flowchart summarizes all study procedures.

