NCT05934591 Unique Protocol ID: UIUC IRB 23828

Improving Attendance in Community Wise

Statistical Analysis Plan 6/1/2025

Statistical Analysis Plan

Variables: marital status, education, number of days paid in the past 30 days, job search status, and employment status. For modeling, potential covariates were selected based on their association (p value <0.2) with one or more of the experimental conditions (surveillance, incentivizing intervention attendance, group type) or attendance rate. We allowed for a larger p value cut off given the small sample size. Associations between continuous measures were examined using Spearman correlation coefficients.

Difference in continuous variables between groups were assessed using the Wilcoxon 2-sample test. Differences in the proportion of categorical variables between groups were assessed using the Chi-Square or Fisher's Exact test.

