To test the objective 'What combination of interventions was associated with higher attendance?', we used a logistic regression model to test the association of group type (open vs closed), incentivizing intervention attendance (incentive vs not) and surveillance (under surveillance vs not) with the outcome of attending 50% of sessions or more (vs not). The logistic regression model included main effects, as well as all 2-way interactions and a 3-way interaction using multiplicative terms. The model was adjusted for job search status, sex, race and ethnicity, marital status income, number of days paid in the past 30 days, and employment status. Parameter estimates (coefficients) and their standard errors were reported. Since the outcome for logistic regression model is the log odds of attending 50% or more sessions, parameter estimates (regression coefficients) represent the change in the odds of the outcome on the log scale for a one-unit change in the independent variable (or at one level compared to its referent if continuous). Thus, parameter estimates were transformed by taking the exponent to facilitate interpretation as odds ratio. Exponentiated coefficients are interpreted as the difference in the likelihood (odds) of achieving the outcome between those who received an intervention component compared to those who did not receive it, collapsing (averaging) over levels of the other components and controlling for covariates. To calculate percent change, exponentiated coefficients are compared to the value of one (one means no difference). A value that is greater than one or less than one, indicates that the outcome is more likely or less likely to occur, respectively. Thus, we subtract one from the exponentiated regression coefficient to obtain the magnitude of change in the outcome, and when multiplied by 100 it is a percent change in the outcome.

To test the objective 'Does higher attendance result in less ASM use?' we employed a generalized multiple regression model testing the association of attendance rates (continuous variable), incentivizing intervention attendance (incentive vs not), surveillance (under surveillance vs not) and their 2-way interaction with the outcome of percent of ASM at follow up, adjusting for demographic characteristics and percent of ASM at baseline. We analyzed the intervention components using effect coding (1 vs -

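### No SAP model has sessions attended, the protocol's named primary outcome, as its outcome, and nothing is compared with the protocol's 50%-of-participants target

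*SAP*

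**What the plan says.** **Protocol.** Section 6 states: "As our primary individual level outcome, we will use number of sessions attended to pursue the following aim". The Study AIM that follows describes clinically important attendance as that "with a minimum of 50% of participants attending at least 50% of the intervention". The same section says that the factorial design will "allow us to examine the individual and interactive contributions of each intervention delivery strategy on intervention attendance". Section 7D fixes the range of the count: "They will also be asked to attend 8, two-hour long weekly intervention sessions". Section 7F gives the source: "Intervention attendance will be recorded weekly in RedCAP by the peer facilitator".

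**SAP.** Three modelled analyses are described.

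- The attendance objective uses a logistic regression on the three factors with all interactions, "with the outcome of attending 50% of sessions or more (vs not"). The planned output is coefficients, standard errors and odds ratios.
- The alcohol and substance misuse (ASM) objective uses a negative binomial regression of percent ASM at follow-up. Attendance rate is a predictor.
- The mediation analysis also has percent ASM as its outcome.

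The opening paragraphs use attendance rate to screen covariates and add a general sentence: "Difference in continuous variables between groups were assessed using the Wilcoxon 2-sample test". A similar sentence assigns Chi-Square or Fisher tests to categorical variables. The paragraph on the ASM model leaves group type out because it failed selection criteria, which are not stated.

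**The concern.** The protocol asks two things about attendance: how each delivery strategy changes the number of sessions attended, and whether enough people reach half of the sessions. The SAP answers a third question, namely how each strategy changes the odds of reaching half. It does not say why the named outcome was set aside or which outcome is now primary.

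Timing adds to this. The SAP is dated 6/1/2025, is written in the past tense and already reports that no mediation was found. Nothing in the documents shows that the outcome was settled before the data were seen.

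At stake is the purpose of the pilot, which is to decide which strategies to keep. Group type has already been left out of the ASM model on unstated criteria, and no check of that decision on sessions attended is documented.

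**Working it through.** **1. Outcome of each SAP model**

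| SAP analysis | Outcome | Role of attendance |
|---|---|---|
| Logistic regression | at least 50% of sessions, yes/no | outcome, dichotomised |
| Negative binomial regression | percent ASM at follow-up | predictor (rate) |
| Causal mediation | percent ASM at follow-up | term in the mediation path |

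Models with number of sessions or attendance rate as outcome: 0 of 3. Stated comparisons with the 50%-of-participants target: 0.

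**2. Inputs.** There are 8 sessions, so 50% is 4. N = 128 in a 2³ factorial gives 128/8 = 16 per condition and 128/2 = 64 per factor level. The documents give no power calculation, SD or assumed rate, so there is no design figure to reproduce. The one rate available is from the earlier trial (Protocol Section 6): "only 15% of participants attended 50% of the sessions". Using it here is an assumption. All other rates below are assumptions too.

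**3. An odds ratio does not show whether 50% was reached.** With baseline odds o = p0/(1 − p0), the new proportion is OR·o/(1 + OR·o). The OR needed to reach 50% is (1 − p0)/p0.

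| Baseline p0 | Proportion after OR = 3 | Target | OR needed for 50% |
|---|---|---|---|
| 15% | 0.529/1.529 = 35% | missed | 5.7 |
| 20% | 0.750/1.750 = 43% | missed | 4.0 |
| 30% | 1.286/2.286 = 56% | met | 2.3 |

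The SAP also describes (OR − 1) × 100 as a percent change in the outcome. For OR = 3 that is 200%. Read as a change in the proportion, 20% would become 0.20 × 3 = 60%, which meets the target, when the true value is 43%.

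**4. The share reaching the cut does not fix the count.** If a share q attends at least 4 sessions, the lowest possible mean is 4q (attenders at 4, others at 0). The highest is 8q + 3(1 − q) (attenders at 8, others at 3).

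- q = 15%: 0.60 to 3.75 sessions
- q = 35%: 1.40 to 4.75 sessions

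A contrast of 15% with 35% is therefore logically compatible with a difference in means from 1.40 − 3.75 = −2.35 to 4.75 − 0.60 = +4.15. These are limits, not expected values.

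**5. Power lost by dichotomising, 64 versus 64, two-sided 0.05.** This is a simulation of an 8-session beta-binomial count: 4,000 runs at each concentration of 1, 2 and 5, without clustering or covariates. It compares a Wilcoxon test on the count with a two-proportion test on at least 4 of 8.

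| Share attending at least 4 of 8 | Count | Dichotomy |
|---|---|---|
| 30% vs 50% | 80–81% | 65% |
| 40% vs 60% | 78–79% | 60–62% |
| 15% vs 50% | over 99% | over 99% |

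**6. What a comparison with 50% could show at the planned size (95% intervals).**

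| Attending at least 4 of 8 | Wilson | Exact |
|---|---|---|
| 32/64 | 38.1–61.9% | 37.2–62.8% |
| 8/16 | 28.0–72.0% | 24.7–75.3% |
| 40/64 | 50.2–73.3% | 49.5–74.3% |
| 12/16 | 50.5–89.8% | 47.6–92.7% |

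The interval lies wholly above 50% from 40/64 or 12/16 by Wilson, and from 41/64 or 13/16 by the exact method. These intervals ignore clustering by group.

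**The case against.** The strongest reply is that this is hardly a switch. The protocol uses sessions attended in order to pursue an aim that is itself worded in terms of attending half of the intervention. The SAP's outcome is computed from the same count at the aim's own cut. That stands as a defence of keeping the logistic model. It does not explain why the named count is left unmodelled, and it does not cover the other half of the aim, the share of participants who reach the cut.

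A second reply is that the Wilcoxon sentence may already cover attendance. With 8 sessions for everyone, rate and count rank alike, and a comparison of two factor levels in a balanced factorial addresses a marginal main effect. That is possible, but the sentence names no attendance endpoint. Such a test would be unadjusted, give no interactions and say nothing about 50%.

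Third, the numbers show possible rather than actual harm. The bounds in step 4 need extreme configurations, and the power loss vanishes for a large effect. The 15% comes from a 15-session, closed-group trial in men with histories of incarceration. The cut-offs in step 6 depend on the interval method. All of this is fair. No particular selection decision has been shown to change.

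Finally, the SAP does speak of odds before its loose percent-change phrase, so that wording is a minor matter. The unstated selection criteria might include the 50% target, but the SAP does not say so.

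**Conclusion.** The concern holds, and it should be fixed. This is settled by the text: no SAP model has the named primary outcome as its outcome, no reason is given, and no estimate is set against the protocol's target. The threshold itself is the protocol's own. The fault is its unexplained use in place of the count.

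The size of the consequence depends on assumptions. Under the assumed beta-binomial counts, the power loss is about 15 to 18 points for the two moderate contrasts and close to nothing for 15% versus 50%. Whether an odds ratio of 3 meets the target depends wholly on the baseline. The attendance data may well support the choices made, but the analyses as described would not let a reader confirm that.

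**What to change.** 1. Add a model of sessions attended (0 to 8) on the three effect-coded factors and all their interactions, with the logistic model's covariates. Linear regression with robust standard errors or a beta-binomial model would serve. Report it as the analysis of the protocol's named primary outcome, labelled as added after results were seen.
2. Keep the logistic model, and state that its outcome departs from the named one and why.
3. Beside it, tabulate the number and proportion attending at least 4 of 8 sessions, with 95% intervals, by factor level and for each of the eight conditions, against 50%. Name the interval method.
4. State the selection criteria, and say whether the group-type decision also holds on sessions attended.
5. Describe (OR − 1) × 100 as a percent change in the odds.

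The cost is one model, one table and some SAP wording, using attendance that was to be recorded weekly. The drawbacks are the post hoc label and wide intervals at 16 per condition. Items 4 and 5 are minor beside the first three.

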We will expand eligibility criteria to include women and people with SUD living in marginalized communities who have not been previously incarcerated. While women comprise a smaller percentage of people with SUD, they experience significant barriers to SUD treatment.⁹ Our pilot study showed that women started the CW intervention with worse outcomes when compared to men but had significantly higher reductions of ASM.¹⁰ While the original CW intervention was developed with and for formerly incarcerated people, it addresses concepts that are relevant to all people with SUD living in marginalized communities. Hence, the 3CB has recommended that we expand our eligibility criteria to reach a more diverse group of people. Our 2^3 full factorial design will examine change in attendance (N=128). Data will be collected at baseline and three months post-baseline. This study will impact public health as it will improve the potency of an optimized multi-level intervention adaptable to address different health inequities.

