1). Thus, the parameter estimates (regression coefficients) that included intervention components were multiplied by a scaling constant of 2 to obtain the main and interaction effects as per guidelines for using effect coding in multiple regression. We did not include group type in this model because group type did not meet our selection criteria for inclusion in the optimized intervention. Due to the skewness of the ASM variable, we assumed a negative binomial distribution, thus we calculated the exponent of these scaled parameter estimates to facilitate interpretation as the percentage of ASM use. For interpretation, exponentiated coefficients are compared to the value of one to estimate a percent change, as was explained for the logistic regression model.

For all models, fit was assessed using standard criteria including the Akaike Information Criterion (AIC), Pearson Chi-Square, and Wald test. Analyses were conducted using SAS version 9.4 (SAS Institute, Cary, NC), using two-sided tests and a significance level of 0.05.

Using the causal mediation approach, we tested the mediation of incentivizing intervention attendance on the relationship between attendance with the outcome of percent of ASM at follow up, adjusting for demographic characteristics and mean percent of ASM use at baseline. Since no mediation effect was noted, no results are shown.

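### The attendance model puts at least 15 parameters on a planned 128 people with no penalised fit, so real effects would be overstated by about 10–25% on the log-odds scale at 30–50% attendance.

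*SAP*

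**What the plan says.** The SAP's attendance analysis is a logistic regression on a binary outcome, "the outcome of attending 50% of sessions or more (vs not"). Its factors are group type, incentive and supervision (called surveillance in the SAP). On model content it says "The logistic regression model included main effects, as well as all 2-way interactions and a 3-way interaction using multiplicative terms". On adjustment it says "The model was adjusted for job search status, sex, race and ethnicity, marital status income, number of days paid in the past 30 days", and then adds employment status. Coefficients are exponentiated and read as odds ratios and percent changes. Testing is done "using two-sided tests and a significance level of 0.05" in SAS 9.4.

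Protocol Section 6 gives the size: "Our 2^3 full factorial design will examine change in attendance (N=128"). The SAP does not give the analysed number, but comments on size when setting its covariate screen: "We allowed for a larger p value cut off given the small sample size".

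Protocol Section 6 also supplies two reference points for the event rate. In the earlier trial, "only 15% of participants attended 50% of the sessions". The target here is "a minimum of 50% of participants attending at least 50% of the intervention".

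Neither document names a penalised or exact method, a rule for empty cells or separation, or a check of events against parameters. Neither gives a power calculation.

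**The concern.** A logistic model with few events per parameter has two known weaknesses under ordinary maximum likelihood. Non-zero coefficients are pushed away from zero. And if the outcome is constant within some combination of the predictors (separation), the likelihood has no finite maximum.

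Both are live here. The factorial part is saturated, so each of the eight cells, about 16 people each, needs both attenders and non-attenders. The covariates then take up more of the same information.

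The study exists to decide which delivery strategies to keep, and this model supplies the answer. Its coefficients go straight into odds ratios and percent changes, so any inflation reaches the reported result. The selection also carries forward: the SAP leaves group type out of the substance-use model because it did not meet the selection criteria.

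**Working it through.** **Plan's own figure.** N = 128 cannot be reproduced, because no effect size or power is given. It is taken as the planned number, 128/8 = 16 per cell.

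**Parameter count.** The factorial part has 1 intercept + 3 main effects + 3 two-way terms + 1 three-way term = 8. The covariates are job search, sex, race/ethnicity, marital status, income, days paid and employment, which is 7. With one column each, 8 + 7 = 15. The documents do not give category counts. Three levels each for race, marital status and employment give 8 + 10 = 18, and finer coding gives 8 + 13 = 21. The figures 18 and 21 are assumptions; 15 is the minimum.

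**Events per non-intercept parameter** = (rate × 128)/(k − 1):

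| Attendance | Events | k = 15 | k = 18 | k = 21 |
|---|---|---|---|---|
| 15% | 19.2 | 1.37 | 1.13 | 0.96 |
| 30% | 38.4 | 2.74 | 2.26 | 1.92 |
| 40% | 51.2 | 3.66 | 3.01 | 2.56 |
| 50% | 64.0 | 4.57 | 3.76 | 3.20 |

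**Empty or full cells.** With the same rate p in all cells, P(at least one) = 1 − (1 − (1 − p)^16 − p^16)^8.
- p = 0.15: 0.85^16 = 0.0743, so 1 − 0.9257^8 = 46%.
- p = 0.30: 0.70^16 = 0.0033, so 1 − 0.9967^8 = 2.6%.
- p = 0.50: effectively 0.

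If one component has an odds ratio of 3, its four lower cells are emptier. At 15% overall the cell rates are 0.084 and 0.216, and 1 − (0.755^4 × 0.980^4) = 70%. At 30% overall they are 0.189 and 0.411, and the chance is 13%.

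With reference coding, which coefficients diverge depends on which cell is empty. With effect coding in the saturated part, all of them do. The SAP does not settle the coding for this model: it describes effect coding only after introducing the substance-use model.

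**Simulation of the SAP model.** N = 128, balanced 2^3 with all interactions, one component with an effect, covariates with no true effect, 500–1,000 runs per setting. Maximum-likelihood summaries use only runs with a finite solution.
- *Inflation of the log odds ratio, true OR 3, k = 18, effect coding:* +14% at 30% attendance, +22% at 40%, +20% at 50%. As odds ratios, 3^1.14 = 3.5 and 3^1.22 = 3.8. Across k = 15–21 and both codings the range is +8% to +26%. A separate simulation gave about 3.9 at 50%.
- *True OR 2, k = 18:* +15% at 30%, +13% at 50%.
- *True OR 1:* no bias. Type I error was 7.3% at 50% and 5.2% at 30%; other simulations of the same model gave 6–9% over 30–50%.
- *Coverage of the 95% interval:* about 92% at 40–50% with effect coding. With reference coding it stayed near nominal (93–96% at 30–50%, k = 18–21).
- *No finite solution, k = 18:* 60% (OR 1) to 75% (OR 3) of runs at 15% attendance, 6–16% at 30%, about 1% or less at 50%.

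**Source of each problem.** With the covariates removed (8 parameters, OR 3), inflation fell to 5% at 30% and 8% at 50%, but 73% of runs still separated at 15%. So the covariates drive most of the inflation, and empty factorial cells drive most of the separation.

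**Firth on the same full model.** It gave an estimate in every run. At k = 18 the mean coefficient was 0.93–1.07 times the truth at all attendance rates. In a further run with all covariates, the average OR was 3.03 at both 30% and 50%, with type I error 3.4–4.4%; another put type I error at about 5%.

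**The case against.** Several objections have force.

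*The SAP looks back.* It is written in the past tense, and the sponsor already knows the attendance rate and whether the model converged. A reader might infer from the separation rates that the reported fit failed. The documents do not show that.

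*15% is a poor forecast.* It comes from a 15-session trial in men with incarceration histories, and Protocol Section 6 puts it down partly to closed groups and the randomisation strategy. This trial has 8 sessions, pays half the sample to attend and tests open groups. The objection stands: 15% marks the low end only.

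*False retention.* A reader might infer that at low attendance a weak component would look worth keeping. The figures point the other way. At 15%, rejection under no effect was about 1–2%, and with a true OR of 3 only about 8%.

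*Cutting the covariates.* The parameter count invites the conclusion that most of them should go. That is not supported. Firth with all covariates already removes the bias. The precision gain from cutting was seen with covariates that were pure noise, whereas the SAP screened covariates for association (p < 0.2) with attendance or an experimental condition. With moderately prognostic covariates (assumed log odds ratios of about 0.5–0.6), a sex-only Firth model averaged 2.5–2.6 against a conditional 3.0, because it targets a different odds ratio. Supervision is also a status filled by quota (Protocol Sections 7F, 10A and 10D) and cannot be assigned, so that contrast may need adjustment.

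*Maximum likelihood is not stated.* True. It is inferred from plain logistic regression in SAS 9.4 with no other method named. If another was used, the SAP should say so.

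**Conclusion.** The concern holds as a moderate estimation weakness that is cheap to correct. With at least 15 parameters and a planned 128 people, default maximum likelihood would overstate real effects by about 10–25% on the log-odds scale at 30–50% attendance. Type I error would be about 6–9%, and interval coverage would drop to about 92% under effect coding. Null effects are not biased.

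Failure to reach finite estimates is a minor risk at the 50% target, a moderate one at 30% and a common one at 15%.

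This rests on four assumptions: maximum likelihood was used; the covariates take about 15–21 parameters in all; about 128 people were analysed; and cells were balanced. A smaller analysed N would make both problems worse.

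**What to change.** Re-fit the same attendance model with Firth penalised likelihood (the FIRTH option in PROC LOGISTIC) and profile-likelihood confidence limits. Keep all seven factorial terms and the listed covariates. Report it beside the existing fit, and label it as added after the original analysis.

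State in the SAP the estimation method, the analysed N, attenders and non-attenders in each of the eight cells, the coding of the factors and of each covariate, and whether any cell was empty or any separation warning appeared.

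The cost is one procedure option, a re-run on existing data and a few lines of text. The statistical price is slight shrinkage of the estimates. No new data are needed.

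### The SAP calls (odds ratio − 1) × 100 from the attendance model a percent change in the outcome; it is a percent change in the odds, and its distance from the change in the proportion attending depends on attendance and on coding that the SAP does not state

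*SAP*

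**What the plan says.** The SAP's attendance objective is analysed by logistic regression. The outcome is binary: attended 50% or more of sessions, or not. The predictors are group type, incentive and surveillance (the protocol's supervision), all their interactions, and covariates. The SAP says that "parameter estimates were transformed by taking the exponent to facilitate interpretation as odds ratio".

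Three statements on interpretation follow in the same paragraph:

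- "Exponentiated coefficients are interpreted as the difference in the likelihood (odds) of achieving the outcome" between those with and without a component, averaged over the other components.
- A value above or below one "indicates that the outcome is more likely or less likely to occur, respectively".
- One is subtracted from the exponentiated coefficient to give the size of the change, and "when multiplied by 100 it is a percent change in the outcome".

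For this model the SAP describes coefficients, standard errors and exponentiated coefficients. It describes no predicted proportion, risk ratio or risk difference.

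The aim in Protocol Section 6 is on the proportion scale: clinically important attendance, "with a minimum of 50% of participants attending at least 50% of the intervention".

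**The concern.** For a binary outcome, a percent change in the outcome is naturally read as a relative change in the proportion who achieve it. An odds ratio minus one is close to that only when the outcome is rare. Here the protocol hopes that at least half of participants will achieve it.

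The pilot is meant to inform which delivery strategies are kept and to support a larger grant application (Protocol Section 6). A reader given only a percentage under this rule cannot tell how far a component moves attendance towards the 50% goal, and is likely to misjudge its size.

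The SAP also carries the rule over to the negative binomial model for alcohol and substance misuse (ASM). There the exponentiated coefficient is a ratio of means, so a percent-change reading is acceptable. The two models are described as if the rule meant the same thing in both.

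**Working it through.** The documents give no odds ratio, percent change or attendance rate by arm for this trial, so there is no stated figure to reproduce. The check is algebra plus an illustration.

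**Inputs.** Protocol Section 6 gives two proportions. In the earlier 15-session trial "only 15% of participants attended 50% of the sessions". The goal now is "a minimum of 50% of participants attending at least 50% of the intervention". All other proportions below are assumptions.

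**Formulas.** Let p0 and p1 be the proportions attending with the component off and on.

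- OR = [p1/(1 − p1)] / [p0/(1 − p0)], so OR − 1 = (p1 − p0) / [p0(1 − p1)].
- RR = p1/p0, so RR − 1 = (p1 − p0)/p0.
- Hence (OR − 1)/(RR − 1) = 1/(1 − p1), whatever p0 is.

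**At the protocol's two figures (15% to 50%).** OR = (0.50/0.50)/(0.15/0.85) = 5.667, so the SAP rule gives +467%. RR = 0.50/0.15 = 3.333, so the relative change in the proportion is +233%, or 35 points. The factor is 1/(1 − 0.50) = 2.00.

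**Range, taking the exponentiated coefficient as the full on-versus-off odds ratio.**

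| p0 | p1 | OR | SAP rule | Relative change in proportion | Difference (points) | Factor |
|---|---|---|---|---|---|---|
| 10% | 15% | 1.588 | +59% | +50% | +5 | 1.18 |
| 15% | 30% | 2.429 | +143% | +100% | +15 | 1.43 |
| 15% | 50% | 5.667 | +467% | +233% | +35 | 2.00 |
| 40% | 60% | 2.250 | +125% | +50% | +20 | 2.50 |
| 50% | 40% | 0.667 | −33% | −20% | −10 | 1.67 |

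**Dependence on coding.** The SAP states 1/−1 effect coding and multiplication by 2 only in its text on the ASM model. For the logistic model it states neither, although the reading of effects as averages over the other components suggests effect coding. Under 1/−1 coding the on-versus-off log odds ratio is 2b, so an unscaled exp(b) is the square root of the odds ratio:

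- 15% to 50%: √5.667 = 2.380, so the rule gives +138% against +233%, an understatement (0.59-fold).
- 40% to 60%: √2.25 = 1.5, so the rule gives +50% against +50%, equal by coincidence.
- 50% to 70%: OR = 2.333 and √2.333 = 1.528, so the rule gives +53% against +40%, an overstatement.

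Under unscaled coding, then, even the direction of the discrepancy is not fixed.

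**The case against.** The strongest reply is that this is loose labelling, not a wrong analysis. The paragraph refers to log odds, odds and odds ratio before it reaches the percent change, and it describes the model's outcome as the log odds. On that reading a change in the outcome means a change on the odds scale. Coefficients and standard errors are to be reported, so a reader who knows the coding can recover the odds ratio. No estimate, sign or p-value changes.

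Much of that stands: the fitted model and its tests are not in question. But the paragraph equates likelihood with odds, then speaks of the outcome as more or less likely, and drops odds from the sentence that defines the reported percentage. The references to odds higher up in the SAP's paragraph do not repair that sentence.

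Two limits on the arithmetic also stand. First, the 50% is a goal and the 15% comes from an earlier trial, so neither is this trial's attendance. Second, the SAP's odds ratio is adjusted for covariates, and a conditional odds ratio does not convert to marginal proportions by the crude formula. The table illustrates the discrepancy and does not estimate it.

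A reader might infer that the SAP overstates the attendance effect two-fold, or that component selection was distorted. The documents support neither. Two-fold needs both p1 = 50% and a full odds ratio. The SAP mentions selection criteria for the optimised intervention but does not give them, and nothing shows that this percentage was used.

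**Conclusion.** The point holds as one of interpretation and reporting on the attendance objective. The SAP's rule yields a percent change in the odds of attending at least half of the sessions, and calling it a percent change in the outcome is wrong as written.

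Its size is conditional. With a full on-versus-off odds ratio, the rule exaggerates the relative change by 1/(1 − p1) in the crude case, which is about 1.2 to 2.5 for p1 between 15% and 60% and exactly 2 at the protocol's target. With unscaled effect coding it could understate. Because the SAP shows no results for this model, no particular misreported number can be identified.

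**What to change.** 1. Call (OR − 1) × 100 a percent change in the odds, and remove the wording that equates odds with likelihood.
2. State the coding of the three components in the logistic model, and whether coefficients were multiplied by 2 before exponentiation.
3. From the same fitted model, report the standardised proportion attending at least 50% of sessions (4 of the 8 in Protocol Section 7D) at each level of each component. Give risk differences with 95% confidence intervals by the delta method, or by bootstrap if it is stable. With 128 planned participants over eight conditions (128/8 = 16 per cell) and covariates in the model, that stability should be checked.

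Step 3 also deals with the adjusted odds ratio, because standardisation averages predicted probabilities over the covariates. Components can then be set directly against the 50% goal. The cost is a few sentences in the SAP and one post-estimation step in SAS. No new data or refitting is needed, and the hypothesis tests stay as they are.
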